3.5 Study Schedule

	Visit 1 Baseline Exam	Visit 2 Procedure	Visit 3 Day 3	Visit 4 Day 5	Visit 5 Week 1	Visit 6 Month 1	Visit 7 Month 3
Forms							
Consent and Authorization form	X						
Baseline form	X						
Procedure form		X	X	X			
IND-VFQ							X
Follow-up form			X		X	X	X
Final form							X
Procedures							
Intrastromal		X	X	X			
Smear/culture	X		X		X		
Tests							
IOP	X		X			X	X
Topography							X
OCT	X					X	X
Slit lamp photography*	X					X	X
BSCVA/ETDRS/MRx	X					X	X
Endothelial cell count							X
Total visit time	2 hours	2 hours	2 hours	2 hours	1 hour	1 hour	1 hour
* Slit lamp photography also taken upon an adverse event							

3.6 Adverse Events (AEs)

During each study visit, the subject will be questioned about AEs in a non-leading manner. All AEs, whether observed by the Investigator, elicited by the Investigator, or spontaneously reported by the subject, will be documented in the subject's chart and the adverse event form. Slit lamp photography will also be completed after any adverse event takes place.

All AEs should be followed until they are resolved or until a stable clinical endpoint is reached. Each AE is to be classified by the Investigator as SERIOUS (SAE) or NONSERIOUS (NSAE).

If a SAE occurs, the investigator at Aravind Eye Hospital, Pondicherry must fill out the serious adverse event form and email it to [name] at UCSF within 24 hours of the occurrence of the SAE. The investigator must provide written follow-up reports until the SAE or clinically significant AE has resolved or until a stable clinical endpoint is reached. Notification of an SAE or clinically significant AE must also be submitted to the Institutional Review Board (IRB)/Ethics Committee (EC) in accordance with its requirements. All AEs must be reported from the time that the subject provides informed consent through the last study visit.

4. PROCEDURES

4.1 Masking

All study participants will be masked to their intervention. The refractionist performing the BSCVA will also be masked. Due to the nature of the intervention, the surgeon and technician performing intrastromal injection will not be masked, however, the physician performing repeat scraping as well as the microbiologist will be masked to treatment arm. UCSF study personnel will not be given any identifying information.

4.2 Ulcer Classification

Factor	Mild	Moderate	Severe
Location	Nonaxial	Central or peripheral	Central or peripheral
Area	2 mm	2–6 mm	≥6 mm
Depth	Superficial one third of stroma	Superficial two thirds of stroma	Extending to inner one third of stroma and/ or endothelial plaque

Any two of three criteria should be fulfilled.

4.3 Medical management protocol

In the first 3 days all patients will receive hourly 5% Natamycin, 0.5% Moxifloxacin for prophylaxis every two hours while awake, and 2% homatropine TID. They will be randomized to intrastromal injection with voriconazole versus sham injection. This study requires 7 visits over 3 months including baseline visit, procedure visit, 3-day follow-up and procedure visit, 5-day procedure visit, 1-week follow-up, 1-month and 3-month follow-up. After the 3-day repeat culture visit additional treatments may be added per clinician preference including but not limited to topical voriconazole and oral Ketoconazole.

4.4 Procedures

4.4.1 Corneal Gram Stain and Culture

After patient history and slit lamp examination at the enrollment visit (Day 0), corneal scraping is performed to determine the eligibility of the patient (positive fungal stain and negative bacterial stain). Corneal scraping is recommended as standard of care for all corneal ulcer patients at the Aravind Eye Hospitals. There is a small risk to patients of inducing a perforation, worsening an epithelial defect, or contaminating an ulcer, and patients are duly informed of these risks prior to the taking of the corneal scrape.

Corneal scraping will be obtained as follows:

- A drop of topical anesthetic (0.5% tetracaine or 4% lidocaine) is administered to the eye to be examined.
- Aseptic technique is used to obtain each corneal scrape. A flame-sterilized Kimura spatula is used, with the aid of slit lamp magnification, to obtain a scrape from the leading edge and base of the corneal ulcer. The Kimura spatula is again flame sterilized between the takings of each sample.
- Two scrapings are smeared directly on to two separate glass microbiology slides for Gram stain and for KOH wet mount (if necessary, Giemsa or Gram Stain can be used to identify fungal elements as well).
- Three further scrapings are taken and directly inoculated on to sheep's blood agar, chocolate agar, potato dextrose agar or Sabouraud's agar for bacterial and fungal culture.

4.4.2 Intrastromal Voriconazole Injection

The intrastromal injection will be performed in the operating theatre under the operating microscope by the cornea surgeon under peribulbar anesthesia and with full aseptic precautions. This will be performed within 24 hours of the baseline visit. Voriconazole 0.5 mg/ml solution will be loaded in a 1 ml tuberculin syringe with a 30-gauge needle. With the bevel down, the needle will be inserted obliquely starting in the adjacent uninvolved stroma to reach the infiltrate at the mid-stromal level (as the intended level for drug deposition) in each case. The drug is then injected and the amount of hydration of the cornea is used as a guide to assess the area saturated with medication. Once the desired amount of hydration is achieved, the plunger is withdrawn slightly to ensure discontinuation of the capillary column and thus prevent back-leakage of the drug. Four to six divided doses are given around the infiltrate/s to surround the entire circumference of the lesion.

4.4.3 Additional Injections

An additional two rounds of intrastromal injections will be performed at 3 days and 5 days post enrollment in the voriconazole injection arm only. This MUST be performed after the 3-day repeat culture visit. The study coordinator and treating physician will be aware of the treatment assignment; however, the follow-up physician and microbiologist will remain masked to treatment arm.

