Studies of intrastromal injection of voriconazole have yielded mixed results. Several case series have found intrastromal voriconazole to be beneficial.¹⁰⁻¹² However, one randomized controlled trial, comparing intrastromal injection to topical voriconazole found significantly improved 3-month visual acuity in the topical voriconazole group.¹³ However, in the intrastromal voriconazole arm there were more central ulcers than in the topical voriconazole arm and scar size between the two groups was comparable implying that intrastromal injection does not lead to worse scarring. In this study we will evaluate the effectiveness of intrastromal voriconazole injection in addition to topical natamycin treatment for the treatment of moderate to severe fungal keratitis.

Research Question: Is intrastromal injection of voriconazole beneficial in addition to topical natamycin in the treatment of filamentous fungal corneal ulcers?

1.1 Specific Aims:

- 1) **Does the addition of intrastromal injection of voriconazole decrease the rate of repeat 3-day culture positivity compared with medical management?** We hypothesize that there will be decreased 3-day repeat culture positivity in the intrastromal voriconazole injection group.
- 2) **Does intrastromal injection of voriconazole improve best spectacle corrected visual acuity at 3 months compared with medical management?** We hypothesize that intrastromal injection with voriconazole will improve 3-month visual acuity compared with topical natamycin alone.
- 3) **Does the addition of intrastromal injection of voriconazole improve 3-month scar size, days to re-epithelialization and rate of perforation/need for Therapeutic penetrating keratoplasty (TPK) compared with medical management?** We hypothesize that there will be improved 3-month scar size and decreased perforation rate in the intrastromal voriconazole group, but no difference in days to re-epithelialization.

1.2 Study Outcomes:

Primary Outcome:

- Microbiological cure on 3-day repeat cultures

Secondary Outcomes:

- BSCVA at 3 months
- Microbiological cure on 7-day repeat cultures
- Scar size/depth, as measured by clinical exam, slit lamp photographs and OCT
- Adverse events including rate of perforation/need for TPK
- Thinning as measured by pachymetry and OCT
- Topography
- Difference in IND-VFQ at 3 months between groups
- Corneal neovascularization, as measured by clinical exam & slit lamp photographs

1.3 Study Design:

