3.4 Study visits

3.4.1 Baseline Visit. During this visit, eligible patients at Pondicherry will be enrolled in the study and will give consent. The baseline patient form will be completed and BSCVA obtained. All study participants will begin topical therapy with hourly 5% natamycin immediately. They will have baseline photography and OCT. They will then be randomized to either intrastromal voriconazole plus natamycin or topical natamycin alone. Those randomized to intrastromal injection will undergo this procedure in the operating theatre within 24 hours. They will have an additional 2 stromal injections: one on the 3rd day and one on the 5th day. All patients will be admitted to the inpatient setting until the 7th day.

3.4.2 Procedure visit. Within 24 hours of the baseline visit study participants randomized to intrastromal voriconazole will undergo injection in the operating theatre. They will have 2 additional rounds of intrastromal voriconazole injections: one on the 3rd day and one on the 5th day of the study.

3.4.3 Day 3 visit. During this visit, study participants will have slit lamp examination and undergo repeat scraping and culture of the corneal ulcer. Adverse events will also be assessed and recorded. Thereafter, all additional treatments including but not limited to topical voriconazole, or oral ketoconazole, will be at the clinician's discretion. The treating physician will remain masked to treatment arm. After the scraping and culture have been performed, participants randomized to receive intrastromal voriconazole injections will receive an additional injection of voriconazole in the operating theatre.

3.4.5 Day 5 visit. On day 5 participants randomized to receive intrastromal voriconazole injections will receive their final injection of voriconazole in the operating theatre.

3.4.6 Week 1 visit. Approximately one week from enrollment patients will undergo repeat scraping and culture. No other study visit information will be gathered during this visit, therefore any further examination, testing, or treatment will be at the discretion of the treating physician. After the Day 7th day, patients may be discharged from the inpatient setting.

3.4.7 One Month visit. During this visit, study participants will have their BSCVA, slit lamp examination, and OCT performed during this visit. Photography will also be performed. Adverse events will be reviewed and recorded.

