4.4.4 TPK

For patients requiring TPK, the corneal button will be sent to microbiology and pathology. Patients should be photographed prior to surgery.

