5.1 Treatment schedule for study medications

In the first 3 days all patients will receive hourly 5% Natamycin drops, 0.5% Moxifloxacin drops for prophylaxis every two hours while awake, and 2% homatropine drops TID. The aforementioned drugs will be used for FDA approved indications. Study participants will then be randomized to intrastromal injection with voriconazole plus natamycin versus natamycin. All medications will be protected and only appropriate personnel will administer the drugs.

Table 2: Dosing schedule for Medications

Medication	Day 1-3	Day 1 Procedure	Day 3 Procedure	After Day 3 Scraping	Day 5 Procedure
Natamycin 5%	Every hour			Physician determined	
Moxifloxacin 0.5%	6 times/day			Physician determined	
Homatropine 2%	3 times/day			Physician determined	
Voriconazole 0.5 mg/ml		50mg/0.1ml administered via intrastromal injection	50mg/0.1ml administered via intrastromal injection	Physician determined	50mg/0.1ml administered via intrastromal injection

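### The protocol gives opposite masking for the treating physician (3.4.3 against 4.4.3), which could bias secondary outcomes that depend on care after Day 3

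*Protocol*

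**What the plan says.** Four parts of the protocol bear on who knows the arm and who directs care.

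- **Section 3.4.3 (Day 3 visit)** hands additional treatment to the clinician once the repeat scraping is done, and then adds: "The treating physician will remain masked to treatment arm".
- **Section 4.4.3 (Additional Injections)** says: "The study coordinator and treating physician will be aware of the treatment assignment". The same sentence keeps a separate follow-up physician and the microbiologist masked.
- **Section 3.4.6 (Week 1 visit)** says that "any further examination, testing, or treatment will be at the discretion of the treating physician".
- **Section 4.1 (Masking)** says that "the surgeon and technician performing intrastromal injection will not be masked", and that "the physician performing repeat scraping as well as the microbiologist will be masked to treatment arm". Participants and the refractionist are also masked. The treating physician is not mentioned.

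Table 2 in section 5.1 marks all four study drugs "Physician determined" after the Day 3 scraping and does not say which physician. Section 4.3 likewise refers only to clinician preference.

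On TPK, section 1.2 lists as a secondary outcome "Adverse events including rate of perforation/need for TPK". Section 4.4.4 deals with specimens and photographs: "For patients requiring TPK, the corneal button will be sent to microbiology and pathology". It names no decision-maker. SAP section 5 uses the acuity measured before surgery as the 3-month value for participants who perforate or undergo TPK.

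**The concern.** Two current sections give one job title opposite masking, and a third gives that title control of treatment. The section meant to settle masking, 4.1, leaves the title out.

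From Day 3 to Month 3 the regimen is discretionary. If the person exercising that discretion knows the arm, care can differ between arms for reasons other than the eye's condition. Section 6.3 says that intrastromal voriconazole alongside oral and topical antifungals is current practice at the hospital, so a physician who knows that an eye has had no injection has an understandable reason to manage it differently.

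The outcomes at stake are the 7-day culture, perforation or need for TPK, and 3-month best spectacle-corrected visual acuity (BSCVA). A TPK decision would count twice, once as an event and once by fixing which acuity value enters the BSCVA comparison.

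**Working it through.** No figure in the plan depends on this point, so the check is a comparison of texts.

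**1. Is the conflict literal?** Yes. Section 3.4.3 makes the treating physician masked and 4.4.3 makes the treating physician aware. Neither document defines the term.

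**2. Does another section resolve it?** No. The roles compare as follows.

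| Role | 3.4.3 | 4.1 | 4.4.3 |
|---|---|---|---|
| Injecting surgeon and technician | not stated | unmasked | not named |
| Physician doing the repeat scraping | not stated | masked | not named |
| Follow-up physician | not named | not named | masked |
| Treating physician | masked | not named | aware |
| Microbiologist | not stated | masked | masked |

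**3. Which reading is likelier?** Three features suggest that 4.4.3 means the injecting surgeon. It is the section on injections. It sets the aware person against a masked follow-up physician. And among physicians, 4.1 unmasks only the surgeon who injects. In 3.4.3, the sentence on masking directly follows the one granting discretion, so 3.4.3 alone puts discretion with a masked physician.

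**4. What follows if 4.4.3 is taken at its word?** The treating physician knows the arm, and 3.4.6 gives that same title discretion at Week 1. Sections 3.4.3 and 4.3 and Table 2 do not prevent this, because they say only clinician or physician.

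**5. Which outcomes are exposed?**

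- *Day 3 culture (primary):* not exposed by this route. Sections 4.3 and 5.1 fix the topical regimen for the first 3 days. Discretion and the second injection come after the scraping, and both the scraping physician and the microbiologist are masked.
- *7-day culture:* exposed. Antifungals may be added between the two cultures.
- *Perforation or need for TPK:* exposed through the choice of antifungals, and more directly if an arm-aware physician also sets the TPK indication. The supplied text does not say who sets it.
- *3-month BSCVA:* exposed through treatment, and through the carried-forward value after TPK.

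**6. Do existing safeguards cover it?** Not fully. The masked scraping physician, microbiologist and refractionist protect how results are obtained, not how treatment is chosen. Intention-to-treat analysis keeps every eye in its assigned arm but does not remove differences in co-treatment caused by knowledge of the arm.

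**7. Can direction or size be derived?** No. Adding antifungals sooner in control eyes would tend to shrink a true benefit. A lower threshold for TPK in control eyes would tend to inflate one. The documents give neither a TPK rate nor a frequency of arm-aware decisions.

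**The case against.** The strongest reply is that this is one wrong word. If 4.4.3 means the injecting surgeon, the two sections describe two people, nobody has contradictory masking, and discretion after Day 3 already lies with a masked physician. The harm then needs a site to prefer 4.4.3 to 3.4.3, and even so it reaches only secondary outcomes.

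Most of that stands. The surgeon reading is the likelier one, and the primary outcome is safe from this route. What does not follow is that the wording can be left alone. The label is undefined, 4.1 is silent on it, and 3.4.6 uses the same label for the person directing treatment.

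Three stronger readings are tempting, and the documents do not support them.

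- *That the trial lets an unmasked physician direct care.* The text permits this if 4.4.3 is followed literally. It does not show that it was intended or that it happened.
- *That an unmasked surgeon decides on TPK.* Section 4.4.4 is silent on who decides. That is a separate omission, not part of the contradiction, and it can be claimed only for the supplied text. Some protocol pages are not available, and neither is the manual of procedures that the SAP cites for cultures.
- *That the long discretionary period measures the bias.* Its length would be the same if every decision-maker were fully masked, so it says nothing about arm-aware care.

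A further fair objection is that a strict rule keeping the injecting surgeon out of TPK decisions could obstruct urgent surgery. That stands, and the remedy below avoids it.

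**Conclusion.** The inconsistency is real, sits in current protocol text and should be corrected. It is probably a wrong term in 4.4.3 rather than a deliberate design choice. If 4.4.3 were followed as written, a physician who knows the arm could choose antifungals after Day 3. That could bias the 7-day culture, perforation or need for TPK, and 3-month BSCVA. The bias could favour either arm, and no size can be given from the documents. The Day 3 primary outcome is not affected.

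The conclusion assumes that the missing pages and the manual of procedures do not define the treating physician. Even if they do, 3.4.3 and 4.4.3 would still need to be reconciled. Confidence in the textual conflict is high. How much it matters in practice depends on which section the site follows, which the documents do not show.

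**What to change.** 1. In 4.4.3, replace the treating physician with the injecting surgeon, matching the unmasked list in 4.1.
2. In 4.1, add the treating or follow-up physician to the masked list, and use one term for that role throughout.
3. In 3.4.3, state that this masked physician chooses any add-on antifungals after the Day 3 scraping.
4. In 4.4.4, state that, where feasible, the masked physician also makes and records the indication for TPK, and that any unmasking is logged. The surgeon should remain free to act in an emergency.

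The cost is a few words in four sections, with no added participants, visits or procedures. The practical burden is that the masked physician must be available for inpatient decisions on Days 3 to 7. Masking may still be incomplete. Section 4.3 mentions a sham injection, but 4.4.3 limits the repeat rounds to the voriconazole arm, so an attentive inpatient physician may notice the theatre visits on Days 3 and 5. The change reduces arm-aware decisions but cannot guarantee their absence.

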4.4.4 TPK

For patients requiring TPK, the corneal button will be sent to microbiology and pathology. Patients should be photographed prior to surgery.

4.5 Anterior Segment Optical Coherence Tomography Protocol

OCT will be documented at baseline, 1 and 3 months. The images will be captured with the Visante using standardized protocols by study certified ophthalmic technicians. The data will then be shared with UCSF via Dropbox.

4.5.1 OCT Scan Procedures

In order to obtain the highest quality anterior segment optical coherence tomography (OCT), the technician will scan the appropriate study eye according to the Visante instruction manual.

All OCT scans will be performed in a designated diagnostic room with a uniform ambient light level.

An initial scan of the global pachymetry will be obtained. Three scans should then be obtained at the pupillary geometric center on the Quad setting (4 line scans through the cornea). Subsequently, a dense scan centered over the area of greatest thinnest (as determined by the global pachymetry) will be performed using the Quad setting. Quantitative data will be obtained using the caliper function by an examiner masked to the results of clinical examination.

4.5.2 Saving Scan

- Save the raw images on the Visante OCT machine
- Download PDF images and save to a USB drive
 - Images over the area of thinning should include the caliper measurement
- De-identify images
 - Patient names or any other identifying information such as birthday should not appear within any of the image files.
- Rename data
 - The image files will be designated with: 1) the study ID number, 2) the timing of visit '1d', "1m", or '3m' respectively for the 1 day, 1, and 3-month follow-up visits, and 3) image number of the series. An image renamed to C101_3m_1.jpg will be the first image for eye number C101's 3 month follow-up visit. An image renamed to C222_1m_3.jpg will be the third image for eye 222's 12 month follow-up visit.
- Batch upload images to Dropbox. Procedures for uploading images to Dropbox:
 - Navigate to Dropbox → eye's folder → relevant study visit
 - Upload images to the eye's relevant study visit folder

5. STUDY MEDICATIONS

The following medications will be administered for treatment purposes: Natamycin 5%, Moxifloxacin 0.5%, Homatropine 2%, and Voriconazole 0.5mg/ml injection.

5.1 Treatment schedule for study medications

In the first 3 days all patients will receive hourly 5% Natamycin drops, 0.5% Moxifloxacin drops for prophylaxis every two hours while awake, and 2% homatropine drops TID. The aforementioned drugs will be used for FDA approved indications. Study participants will then be randomized to intrastromal injection with voriconazole plus natamycin versus natamycin. All medications will be protected and only appropriate personnel will administer the drugs.

Table 2: Dosing schedule for Medications

Medication	Day 1-3	Day 1 Procedure	Day 3 Procedure	After Day 3 Scraping	Day 5 Procedure
Natamycin 5%	Every hour			Physician determined	
Moxifloxacin 0.5%	6 times/day			Physician determined	
Homatropine 2%	3 times/day			Physician determined	
Voriconazole 0.5 mg/ml		50mg/0.1ml administered via intrastromal injection	50mg/0.1ml administered via intrastromal injection	Physician determined	50mg/0.1ml administered via intrastromal injection

